## 5.10 Other Notice to Applicants

To relieve potential risks of photostimulation/phototoxicity, patients should be instructed to avoid strong sunlight, fluorescent lamp and other ultraviolet radiation sources during the study. It is suggested all patients adopt protective skin care measures, including: sunscreen cream with a sun protection factor  $\geq 30$ , hypoallergenic moisturizing cream or ointment suitable for dry skin, cleaning and caring the skin with soaps and detergents not containing perfume.

## 5.11 Channels to access the investigational drug after the end of the trial

The study endpoints and discontinuation criteria are based on disease progression by independent imaging review, so there is no plan to provide investigational drug or other study

intervention to patients after the end of the study or after any patient has withdrawn prematurely. The Sponsor will evaluate the possibility to continue providing DCC-2618 to study patients after the primary study endpoint and safety data collected in the study are evaluated.

## 6 Visit Schedule and Assessments

Visit schedule of the study is shown in Table 1. All times should be recorded in a 24-hour format (e.g., 23:20 other than 11:20 PM).

## 6.1 Screening

Before starting any study-related procedures, the informed consent form signed by the patients must be obtained.

The screening period was limited to 21 days.

For the screening test, if the patient is routinely examined during the diagnosis and treatment of GIST and completed within the corresponding time limit required by the protocol (such as 21-day screening window,7 days before the first dose of investigational drug, etc.), and the test requirements of the protocol are met, The results of these tests may be used as screening assessments if earlier than the informed consent is signed.

## 6.2 Re-screening

Subjects can receive re-screening after obtaining the approval of the sponsor. If patients have received re-screening, except for ophthalmological examination, other assessments in the screening period should be performed again. If radiographic examination and dermatologic examination are performed 21 days prior to the first dose of the investigational drug, the examinations are not need to be performed again. Patients can be re-screened once only. If patients enter re-screening, the screening window will be calculated after the start of the re-screening.

## 6.3 Study period

After confirming patients meet the inclusion criteria, the drug will be administered once on Day -7. Intensive blood collection will be carried out after that. Hospitalization is suggested during intensive blood collection. Continuous administration starts on C1D1 and subjects enter the study treatment period. See Table 1 for visits in the study period. All study visits should be carried out in the window.

All subjects who withdraw treatment should carry out visit at study site within 7 days after the last dose.

## 6.4 Follow-up

All subjects will receive safety follow-up 30 days ( $\pm 5$  days) after the last dose and ask subjects through telephone adverse events after the last dose and drug therapies including

anti-tumor therapy and other treatments.

Survival follow-up should be carried out once monthly after that to ask subjects through telephone survival status and anti-tumor therapy condition.

#### 6.5 Lost to Follow-up

If the following two conditions are met, it will be considered subjects are lost to follow-up:

- The subject has missed two consecutive visits and can't be contacted through telephone after the second missed visit (contacting through telephone for 3 times within 2 weeks).
- After the subject can't be contacted through telephone for 3 times, a registered mail is sent to the subject, but the subject does not reply within 2 weeks.

#### 6.6 Study evaluation

This section will describe special assessments during the study in detail. See Table 1 for conventional assessments.

At any time during the study, if clinically indicated, unscheduled safety and efficacy assessment can be carried out.

#### 6.6.1 Time points assessed

Examinations will be carried out according to time points described in Table 1.

#### 6.7 Informed Consent Form

All patients should sign a written informed consent form before carrying out any procedures. The informed consent form approved by the sponsor, institutional review board (IRB)/independent ethics committee (IEC) should be used. The investigator should record informed consent process, including date of signing the informed consent form.

#### 6.8 Assigned Subject No.

Each patients will be assigned a subject number after signing the informed consent form. If the patient receives re-screening, the original subject number will be used.

#### 6.9 Demographics and Medical History

Demographic data must be collected during the screening period.

Tumor history and prior treatments (including reasons for treatment discontinuation):

- Known GIST histological diagnostic results.
- KIT/ PDGFRA gene mutation status.
- All prior anti-neoplastic therapies, including
- Surgery: including surgery date, site and method (e.g., only tumor tissue samples are

collected or R0, R1 and R2)

- Systemic therapy: including treatment date, drug (including dose and dosing regimen), treatment purpose (e.g., adjuvant therapy or treatment for metastases), best response, date of progressive disease or other reasons and date for treatment discontinuation.
- Radiation therapy: including site, total dose, date and treatment efficacy.
- Other treatments: such as radiofrequency ablation, including site, date and treatment efficacy.

Other medical history: any clinically significant diseases prior to signing the informed consent form should be collected during the screening period to evaluate whether patients have diseases listed in the inclusion and exclusion criteria. Medial history should include review of all organ and system, prior medical and surgical history and allergic history. Diseases that still exist when signing the informed consent form will be regarded as concomitant diseases and the starting date should be recorded.

#### 6.10 Efficacy

## 6.10.1 Radiographic examination

All subjects will receive radiographic examination of the chest, abdomen and pelvis. See Table 1 for arrangement of time points.

Radiographic examination during the Screening Period should cover the chest, the abdomen and the pelvis (within 21 days before the first dose). Only abdomen and pelvis are examined during the study; for patients with pulmonary metastases in the screening period or pulmonary metastases symptoms during the study at the investigator's discretion, chest examination should be performed during the study. It is performed once in each of the first four cycles (including Cycle 4), and then once in every two cycles (e.g., Cycles 6, 8 and 10).

Radiographic examination must be performed within 21 days before the first dose of drug. Radiographic examination performed before signing an ICF can be used in the Screening Period as long as it is performed within 21 before the first dose and the examination method and result comply with the protocol. Radiographic examination can be performed within  $\pm 7$ days of the scheduled visit . On the basis of independent radiology review, patients assessed as CR or PR in the first assessment should undergo confirmation at least 4 weeks later. Enhanced scan should be performed. If subjects are allergic to CT enhancer, MRI can be performed for abdominal and pelvic examinations and CT for chest examinations as long as examination methods are consistent during the study. Ultrasound examination cannot be performed.

If the subject discontinues treatment for reasons other than progressive disease, death, withdrawal of informed consent and lost to follow-up, the subject should receive radiographic

examination for tumor assessment by IRR after treatment withdrawal according to the frequency consistent with that during the study until presence of disease progression meeting "RECIST v1.1-GIST Specific Standard" or until starting of new anti-tumor therapy, whichever is the first.

Copies of all radiographic scans should be obtained and, according to the regulations, sent to the independent imaging supplier designated by the sponsor. The independent imaging supplier will assess imaging quality and be responsible for independent radiology review.

Independent imaging supplier must ensure independent radiology reviewers are blinded to investigator's assessment and other information. Before any independent radiology review, this procedure and all other radiographic images procedures will be recorded in the specified review rules of protocol between the sponsor and the independent imaging supplier.

Independent radiology reviewers and investigators will assess tumor response based on RECISTv1.1-GIST Specific Standard. Response confirmed by investigators will be recorded in the eCRF. Data from independent radiology review will be used for primary endpoint analysis.

**Confirmation of absence of progressive disease:** if independent radiology reviewers confirm there is no progressive disease, the patient will continue to receive treatment with the investigational drug, unless there are medical needs requiring discontinuation of the investigational drug (that is, rapid progression or clinical worsening). If investigators confirm progressive disease according to clinical worsening, scan should be performed and reviewed by independent radiology reviewers to confirm whether the patient has progression. Basis of confirming progressive disease as per clinical worsening should be recorded in patients' source documents and eCRF.

**Confirmation of progressive disease:** subjects who have radiologically confirmed progressive disease on the basis of independent radiology review can continue DCC-2618 treatment at a dose increased to 150 mg, BID; subjects who can benefit from DCC-2618 treatment but cannot tolerate the increased dose will continue DCC-2618 treatment, 150 mg QD; or discontinue DCC-2618 treatment. If subjects use the drug at the original dose, dose escalation will not be performed in the future.

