17. Radiographic examination during the Screening Period should cover the chest, the abdomen and the pelvis (within 21 days before the first dose). Only abdomen and pelvis are examined during the study; for patients with pulmonary metastases in the screening period or pulmonary metastases symptoms during the study at the investigator's discretion, chest examination should be performed during the study. It is performed once in each of the first four cycles (including Cycle 4), and then once in every two cycles (e.g., Cycles 6, 8 and 10). Initial evaluation of CR or PR should be conformed 4 weeks later at least. Enhanced scanning is required for the examination. MRI may be applied to subjects allergic to CT enhancer to examine the abdomen and the pelvis, with plain CT scanning for the chest. Ensure consistency in examination means during the study. No ultrasonic examination is allowed. If the subject discontinues treatment for reasons other than progressive disease, death, withdrawal of informed consent and lost to follow-up, the subject should receive radiographic examination for tumor assessment by IRR after treatment withdrawal according to the frequency consistent with that during the study until presence of disease progression meeting "RECIST v1.1-GIST Specific Standard" or until starting of new anti-tumor therapy, whichever is the first.

Abbreviations	Chinese Terminology
AE	Adverse Event
ALT	Alanine aminotransferase
AML	Acute myeloid leukemia
ANC	Neutrophil count
APTT	Activated partial thromboplastin time
ASM	Aggressive systemic mastocytosis
AST	Aspartate aminotransferase
ATC	Chemical drug classification system
AUC	Area under the concentration-time curve
β-hCG	Human Chorionic Gonadotropin
BCRP	Breast cancer resistance protein
BID	Twice daily
BP	BP
CI	Confidence interval
CL/F	Apparent plasma clearance
C max	Maximum concentration
СРК	Creatine kinase
CR	Complete response
CSF1R	Macrophage colony stimulating factor receptor
СТ	Computed tomography
CTCAE	Common Terminology Criteria for Adverse Events
СҮР	Cytochrome P450
DCR	Disease control rate
DLT	Dose-limiting toxicity
ECG	Electrocardiogram
ECOG	Eastern Cooperative Oncology Group
eCRF	Electronic Case Report Form
EMA	European Medicines Agency
ЕОТ	End of Study Treatment
ESMO	European Society for Medical Oncology
FDA	Food and Drug Administration

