# 9.2 Endpoints of study analysis

# 9.2.1 Primary endpoints

# 9.2.1.1 Efficacy

- Progression-free survival (PFS) based on independent radiologic review: assess PFS according to "RECIST v1.1-GIST Specific Standard" which include:
  - Lymph nodes cannot be taken as target lesions; enlarged lymph nodes will be followed as non-target lesions.
  - Bone lesions cannot be taken as target lesions;
  - Positron emission tomography (PET) cannot be used in efficacy assessment;
  - According to "RECIST v1.1-GIST Specific Standard", new tumor nodules within the pre-existing tumor lesion that are gradually growing must meet the following criteria before being determined as definite progression: (a) The lesion diameter should be at least 2 cm and confirmed as active GIST lesion (for example, using contrast or other criteria for enhanced scanning to rule out the possibility of false appearance); Or (b) At least 2 consecutive radiographic examinations indicative of enlarged lesion.

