# 16 Annexes

# Annex 1 Response Evaluation Criteria in Solid Tumors - GIST Specific Standard (RECISTv1.1-GIST Specific Standard)

"RECIST v1.1-GIST Specific Standard" include:

- Lymph nodes cannot be taken as target lesions; enlarged lymph nodes will be followed as non-target lesions.
- Bone lesions cannot be taken as target lesions;
- Positron emission tomography (PET) cannot be used in efficacy assessment;
- According to "RECIST v1.1-GIST Specific Standard", new tumor nodules within the pre-existing tumor lesion that are gradually growing must meet the following criteria before being determined as definite progression: (a) The lesion diameter should be at least 2 cm and confirmed as active GIST lesion (for example, using contrast or other criteria for enhanced scanning to rule out the possibility of false appearance); Or (b) At least 2 consecutive radiographic examinations indicative of enlarged lesion.

Source: Demetri GD, Jeffers M, Reichardt P, Kang Y-K, Blay J-Y, Rutkowski P, et al. Mutational analysis of plasma DNA from patients (pts) in the phase III GRID study of regorafenib (REG) versus placebo (PL) in tyrosine kinase inhibitor (TKI) refractory GIST: Correlating genotype with clinical outcomes. J Clin Oncol 31, 2013 (suppl; abstr 10503).

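### On-study chest imaging is scheduled only for lung metastases or their symptoms, so baseline chest lesions outside the lung have no scheduled re-imaging

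*Combined protocol and SAP*

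**What the plan says.** **Screening.** Section 6.10.1: "Radiographic examination during the Screening Period should cover the chest, the abdomen and the pelvis". Inclusion criterion 8 requires a measurable lesion but does not restrict it to the abdomen or pelvis.

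**On study.** Section 6.10.1 and Table 1 note 17 both state: "Only abdomen and pelvis are examined during the study; for patients with pulmonary metastases in the screening period", the chest is added. There are two exceptions. One is lung metastasis at screening. The other is "pulmonary metastases symptoms during the study at the investigator's discretion, chest examination should be performed during the study". No other chest site is named.

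**Opening sentence of the same section.** "All subjects will receive radiographic examination of the chest, abdomen and pelvis". It does not limit the chest to screening and refers to Table 1 for timing.

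**Response criteria.** Section 9.2.1.1 and Annex 1: "Lymph nodes cannot be taken as target lesions; enlarged lymph nodes will be followed as non-target lesions". There is no exception for nodes in the chest. Annex 1 adds: "Bone lesions cannot be taken as target lesions".

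**Unscheduled imaging.** Table 1 note 1 lets the investigator order further examinations when clinically indicated. Section 6.6 allows unscheduled efficacy assessments on the same condition. Section 6.10.1 also calls for a scan, reviewed independently, when the investigator diagnoses progression from clinical worsening; it names no body region.

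**The concern.** The baseline lesion list is drawn from three body regions, but the default follow-up covers two. The rule that restores the third is tied to one organ, the lung, and not to whether a lesion was recorded in the chest. A subject can therefore enter with a documented chest lesion that counts toward response and progression and then have no planned scan that shows it.

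The primary endpoint is PFS by independent review (Section 9.4.5.1). Reviewers can assess only the images they receive. Asymptomatic growth of an unscanned lesion would be dated late or not at all, which lengthens PFS. There is no control arm in which the same error would occur. Confirmed ORR (Section 9.4.5.2) and week-12 DCR (Section 9.4.5.3.4) would also rest on incomplete follow-up of baseline disease. The study is meant to show consistency with the global data (Sections 1.4.1 and 9.1), so bias in the estimate matters even if the 1-month hurdle is cleared comfortably.

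**Working it through.** No figure in the plan bears directly on this point, so there is none to reproduce. The check is a reading of the rules, followed by an illustration of size.

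**1. Apply the rules to one case.** Take a subject with an enlarged mediastinal node at screening, no lung metastasis and no chest symptoms.

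- Screening: the chest is scanned and the node is recorded.
- Response criteria: the node must be followed, since "enlarged lymph nodes will be followed as non-target lesions".
- On-study default: abdomen and pelvis only, so the node is outside the field.
- First exception (lung metastasis at screening): not met.
- Second exception (symptoms of lung metastasis): not met.
- Table 1 note 1 and Section 6.6: these permit a scan, but only if clinically indicated.
- Clinical-worsening scan: not triggered while the subject is well.

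So the criteria require follow-up and the schedule does not provide it. The same path applies to a pleural, thoracic bone or oesophageal lesion. Nodes and bone can be affected only as non-target disease; a pleural or oesophageal lesion could also be a target.

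**2. Illustrate the size for PFS.** Inputs: null median 1 month, alternative 2.5 months and two-sided level 0.1, hence one-sided 0.05 with z = 1.645 (Section 9.1); 21 independently reviewed PFS events (one of the two data-cutoff conditions in Section 9). Let f be the share of the PFS hazard that arises at unimaged chest sites. The documents give no value for f, so 1% to 10% is assumed. Under an exponential model in which this share is never detected:

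- observed median = true median / (1 − f)
- one-sided error = 1 − Φ(1.645 − √21 × ln[1/(1 − f)])

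For f = 5%: 2.5/0.95 = 2.63 months. Also ln(1/0.95) = 0.0513, and 0.0513 × 4.583 = 0.235, so the error is 1 − Φ(1.410) = 7.9%.

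| f | True 1.0 month appears as | True 2.5 months appears as | One-sided error (nominal 5%) |
|---|---|---|---|
| 1% | 1.01 | 2.53 | 5.5% |
| 2% | 1.02 | 2.55 | 6.0% |
| 5% | 1.05 | 2.63 | 7.9% |
| 10% | 1.11 | 2.78 | 12.3% |

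The error column uses a log-hazard approximation, not the plan's Kaplan-Meier confidence limit for the median. It shows scale only.

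**3. Compare with the expected effect.** The phase 3 median on ripretinib was 27.6 weeks (Section 1.3.1.3.2). If that were observed here with f = 10%, the true median would be 27.6 × 0.9 = 24.8 weeks, still far above 1 month.

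**4. ORR and DCR.** One subject of 35 is 1/35 = 2.9 percentage points. The direction is not fixed. Unseen chest progression would flatter either rate, while a time point treated as not evaluable could lower it. Annex 1 gives only the GIST-specific modifications and does not say how an unassessed baseline lesion is handled.

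**The case against.** The strongest case against is that the imaging rule is a default and not a prohibition. Unscheduled examinations and efficacy assessments are allowed, a scan follows clinical worsening, and the node rule itself gives a site grounds to scan a known chest node. Section 6.10.1 also defers further image procedures to review rules agreed with the imaging supplier, which are not among these documents. A PFS date shifts only if the chest progresses first, silently, and before any abdominal or pelvic progression. The affected share is therefore smaller than the share of subjects with such lesions.

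Much of this stands. A reader might infer that these lesions are never re-imaged, or that progression there cannot be seen. The documents do not support that, because of the unscheduled-scan provisions. Nor do they support a claim that the ORR error favours the drug. The opening sentence of 6.10.1 is better read as loose drafting than as a competing rule, since it points to Table 1.

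The scheduling gap remains. Every provision cited depends on a clinical indication, on worsening, or on a site choosing to go beyond the schedule. None plans follow-up of a silent, known lesion, and review rules cannot assess images that were not acquired.

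**Conclusion.** The point holds as a scheduling gap and an inconsistency. Subjects whose baseline chest disease is not pulmonary have no scheduled on-study chest imaging, although the response criteria require enlarged nodes to be followed. Asymptomatic progression there could be missed or dated late, and for PFS that error favours the drug.

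The effect is probably small. At an assumed hazard share of 1% to 2%, a 2.5-month median moves by 0.03 to 0.05 month and the one-sided error rises to 5.5% to 6.0%. At 10% the figures are 0.28 month and 12.3%. These rest on an exponential model, 21 events and no rescue by unscheduled scans, so for a given f they lean high. The documents do not say how many subjects, if any, will have such lesions. Given the phase 3 median, reversal of the primary conclusion is unlikely. The change is worth making because it is cheap and aligns the imaging schedule with the response criteria.

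**What to change.** In Section 6.10.1 and Table 1 note 17:

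- Replace the baseline trigger (lung metastases at screening) with any target or non-target lesion in the chest at screening, whether lung, pleura, node, bone, oesophagus or other.
- Broaden the symptom trigger from lung metastases to suspected chest disease.
- Reword the opening sentence of 6.10.1 so that chest imaging for all subjects applies at screening.

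The cost is a change of wording in two places and slightly more radiation for a few subjects. Chest coverage is added to scans already scheduled, with no new visits. The change does not schedule a search for new, silent chest lesions in subjects with a clear chest at screening. If the sponsor accepts that limit, the plan should say so.

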## 6.10.2 Survival follow-up

All subjects should receive survival follow-up until withdrawal of consent inform, lost to follow-up or death for any reasons. After the safety follow-up, the investigator should call the subject to follow-up the survival status and anti-tumor therapy once monthly ( $\pm 5$  days).

## 6.11 Safety

Safety was assessed based on changes from baseline in physical examination, ECOG score, vital signs, ECG, left ventricular ejection fraction, dermatological examination and laboratory

parameters, and reported adverse events.

